6.4 Sample size

(ICH E3; 9.7.2. ICH E9; 3.5)

In the Phase I/II AURA clinical trial, where osimertinib (AZD9291) was administered to patients with advanced EGFR-mutant NSCLC after progression to EGFR TKIs, among the 127 patients with centrally confirmed EGFR T790M mutation, the response rate was 61%. In contrast, amongst 61 patients without centrally confirmed EGFR T790M, the response rate was 21% (15). In the West Japan Thoracic Oncology Group 3405 (WJTOG3405) study, comparing gefitinib with first-line chemotherapy in patients with advanced NSCLC with activating mutations in EGFR, the ORR in the overall population with measurable disease was 62.1% in the gefitinib group and 32.2% in the chemotherapy group. In the North East Japan 002 (NEJ002) study, comparing gefitinib with first-line chemotherapy in patients with advanced NSCLC with EGFR mutations, the gefitinib group had a significantly higher ORR (73.7% vs. 30.7%). In the OPTIMAL study, comparing erlotinib with chemotherapy in patients with advanced NSCLC with EGFR mutations, ORR was 83% for erlotinib and 36% for patients receiving chemotherapy (C. Zhou et al. 2011). In the LUX-Lung 3 study, comparing afatinib with first-line chemotherapy in patients with advanced NSCLC with EGFR mutations, ORR was significantly higher for patients treated with afatinib compared to chemotherapy according to both the independent evaluation committee (56% and 23%, respectively) and the investigator (69% and 44%, respectively) assessments. In the EURTAC study, comparing erlotinib with first-line chemotherapy in patients with advanced NSCLC with EGFR mutations, ORR was 65.1% in the erlotinib group and 16.1% in the chemotherapy group. A subsequent study assessed the impact of pre-treatment presence of the concomitant EGFR T790M mutation. Among patients treated with erlotinib, the presence of this concomitant mutation was evaluated in 95 patients. ORR was found to be 75% in patients without pre-treatment T790M, compared to 47% in patients with pre-treatment T790M.

This data suggests that excluding an ORR $\leq 50\%$ while targeting the improvement of the ORR to $\geq 70\%$ would be a conservative approach to assess the osimertinib (AZD9291) treatment effect in this patient population. Accordingly, this study will test the null hypothesis that the ORR is $\leq 50\%$ against the alternative hypothesis that it is $\geq 70\%$. Applying Simon's optimum 2-stage design (Simon, R 1989), a sample size of 73 patients has power > 0.90 to achieve a 1-sided significance level of 0.025. In the first stage, 21 patients will be accrued. If there are 11 or fewer responses in these 21 patients, the study will be stopped. Otherwise, 52 additional patients will be accrued for a total of 73 patients. The null hypothesis will be rejected if 45 or more responses are observed in 73 patients. This design yields a type I error rate of 0.025 and a power of 90% when the ORR is 70%. The recruitment will be competitive between sites.

6.5 Randomization and blinding

(ICH E3; 9.4.3, 9.4.6. ICH E9; 2.3.1, 2.3.2)

No applicable.

6.6 Interim analysis

An interim analysis will be performed when 21 patients have been assessed up to 42 weeks or withdrawn from the study. The interim analysis will assess the primary endpoint and all the secondary safety and efficacy objectives limited to a window of up to 42 weeks. The first interim report will only include the summary of study accrual, the clinical and demographic summary, the primary efficacy analysis and the report of toxicity. This first report has developed to not delaying the go/not go decision in the first stage. The other results will be presented later. After the database

lock at 42 weeks, these patients will continue to be treated and monitored until progression, death or treatment discontinuation. The decision to stop and continue the trial should be agreed by the steering committee after reviewing the interim safety and efficacy data.

6.1 Final analysis

Upon completion of the interim analysis, and according to the evaluation of the results obtained during the interim analysis, recruitment of patients will resume until a total of 73 patients have been recruited during a 24-month recruitment period. A follow-up lasting up to 78 weeks will begin upon the first dose had been administered to each patient. The study will end, at latest, 78 weeks after last patient has started the treatment.

Number and percentage of patients who obtain Complete Response, Partial Response, Stable Disease and Disease Progression will be provided. The Objective Response Rate (ORR), unconfirmed and confirmed and its 95% confidence interval (CI) will be calculated. The Disease Control Rate (DCR) and its 95% CI will be calculated. Progression-free Survival (PFS), Overall Survival (OS), Time to Treatment Failure (TTF) and Duration of Response (DOR) will be considered secondary objectives, and as they are time objectives, they will be analyzed using the Kaplan-Meier method. The number and proportion of events and median survival time with their corresponding 95% CIs will be calculated. The analyses will be supported by graphical presentations such as survival plots. The average percentage of Tumor Shrinkage (TS) observed from baseline to study visits, with their corresponding 95% CIs, will be calculated.

All efficacy analyses will be exploratory. Positive results in this trial will not confirm treatment efficacy, however, they will indicate that osimertinib (AZD9291) might be considered in the supportive tests.

7.3 Safety analysis:

Analysis of safety-related data will be considered at three levels:

- First, the degree of exposure (dose, duration, number of patients) will be assessed to determine the degree to which study safety can be assessed.
- Second, clinically relevant tests, concomitant medications and reported adverse events for each study group will be described and compared. For adverse events, severity, expectedness, causality, relationship, body system, action taken and outcome will be reported.
- Third, serious adverse events, deaths and study discontinuations for each study group will be described and assessed.

7.4 Analysis populations

(ICH E3; 9.7.1, 11.4.2.5. ICH E9; 5.2)

Full Analysis and Safety analysis set (FAS)

Includes all included subjects who have received any study drug, independently of the degree of adherence to the protocol.

Per Protocol Set (PP)

The Per Protocol set includes all patients included in the FAS who did not violate the protocol in a way that might affect the evaluation of the effect of the study drug on the primary endpoint, i.e., without a major protocol violation.

Major and minor protocol violations will be identified by clinically trained personnel before the database lock. The definition of the major protocol violations is described in **Appendix 2**.

Biomarker analysis set

All patients included in FAS who has been evaluable for biomarker status.

Sensitivity analysis

Primary efficacy analysis will be performed on the full analysis (FAS) and PP sets. Secondary efficacy analysis will be performed on FAS. FAS will be considered the primary population for the efficacy analysis.

Biomarker analysis will be performed on biomarker analysis set.

Safety analysis will be performed on the full analysis set.

7.5 Covariates and subgroups

(ICH E3; 9.7.1, 11.4.2.1. ICH E9; 5.7. CPMP 2002; 4.CPMP 2003.)

Difference between baseline tumor measurements and those observed throughout the study will be analyzed using the Wilcoxon test. Patients with and without different types of EGFR mutation will be compared. For binary outcomes (cORR, ORR and DCR), the chi-square or Fisher's exact test will be used. For time objectives (PFS, OS, TTF and DOR), the Kaplan-Meier method and log-rank test will be used. For continuous objectives (percentage of Tumor Shrinkage, TS), the Mann-Whitney U test will be used.

Baseline biomarker levels will be correlated with the clinical response. For binary and continuous results, the Spearman correlation will be used. For time objectives (PFS), the Kaplan-Meier method and log-rank test will be used. The categorization or log-transformation of biomarker levels will be considered.

The feasibility of re-biopsies at the time of progression will be estimated with the number and percentage of patients with rebiopsy and 95% confidence interval.

The presence of mutations and biomarker levels (tissue or blood) will be compared from baseline to time of progression with the Mc Nemar and Wilcoxon tests, respectively.

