8.2 Efficacy results

Primary Endpoint

We will describe number and proportion of patients with OR (Objective Response) in the first and second stages. We will estimate the proportion of responders with Clopper-Pearson 95% confidence intervals. We will estimate the uniformly minimum variance unbiased estimator (UMVUE), p-value and 95% confidence interval.

Secondary endpoints:

Number and percentage of patients who obtain Complete Response, Partial Response, Stable Disease and Disease Progression will be provided. The Objective Response Rate (ORR) and its 95% confidence interval (CI) will be calculated. The Disease Control Rate (DCR) and its 95% CI will be calculated. Progression-free Survival (PFS), Overall Survival (OS), Time to Treatment Failure (TTF) and Duration of Response (DOR) will be considered secondary objectives, and as they are time objectives, they will be analyzed using the Kaplan-Meier method. The number and proportion of events and median survival time with their corresponding 95% CIs will be calculated. The analyses will be supported by graphical presentations such as survival plots.

Difference between baseline tumor measurements and those observed throughout the study will be analyzed using the Wilcoxon test. The average percentage of Tumor Shrinkage (TS) observed from baseline to study visits, with their corresponding 95% CIs, will be calculated. Patients with and without different types of EGFR mutation will be compared. For binary outcomes (ORR and DCR), the chi-square or Fisher's exact test will be used. For time objectives (PFS, OS, TTF and DOR), the Kaplan-Meier method and log-rank test will be used. For continuous objectives (percentage of Tumor Shrinkage, TS), the Mann-Whitney U test will be used.

Baseline biomarker levels will be correlated with the clinical response. For binary and continuous results, the Spearman correlation will be used. For time objectives (PFS), the Kaplan-Meier method and log-rank test will be used. The categorization or log-transformation of biomarker levels will be considered.

The feasibility of re-biopsies at the time of progression will be estimated with the number and percentage of patients with rebiopsy and 95% confidence interval.

The presence of mutations and biomarker levels (tissue or blood) will be compared from baseline to time of progression with the Mc Nemar and Wilcoxon tests, respectively.

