5.2.3 Exploratory endpoints

The following exploratory endpoints will be analyzed:

- Correlation ratio of mutational status and documented clinical response.

- A progress curve showing the EGFR mutational status (including the T790M mutation) in plasma and serum longitudinally.
- Percentage levels of BIM mRNA as well as mRNA levels of other biomarkers related to EGFR TKI response.
- Percentage of patients with mutations at the site of covalent binding to the drug (C797) or other mutations in tissue and correlation ratio of documented clinical response.

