7.6 Missing data

(ICH E3; 9.7.1, 11.4.2.2. ICH E9;5.3. EMA Guideline on Missing Data in Confirmatory Clinical Trials)

We will report the number of missing values for each endpoint. Patients with missing values in the primary analysis and clinical response outcomes (cORR, ORR and DCR) will be considered non-responders. The analysis of time-dependent secondary endpoints (progressions, treatment failures and deaths) will be based on a log-rank test or on Cox regression tests and therefore, will not be affected by the withdrawal of patients (as they would be censored), provided that withdrawals are not related to the prognosis. Patients with missing data regarding endpoints, such as objective response, will be considered patients with no response to treatment. In addition, we will also report the reasons for withdrawal for each allocated patient.

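### Continuous baseline biomarker levels are tested against PFS by log-rank with no rule for forming the groups; a Cox model on the log level should be the named analysis (low priority)

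*SAP*

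**What the plan says.** The markers are measured as levels. SAP 5.2.3 lists "Percentage levels of BIM mRNA as well as mRNA levels of other biomarkers related to EGFR TKI response", and Protocol 2.2 asks whether such levels predict treatment response.

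SAP 7.5 gives two routes from a baseline level to outcome. For response and other non-time outcomes, "For binary and continuous results, the Spearman correlation will be used". For PFS, "For time objectives (PFS), the Kaplan-Meier method and log-rank test will be used. The categorization or log-transformation of biomarker levels will be considered". Protocol 8.2 has the same closing sentence: "The categorization or log-transformation of biomarker levels will be considered". Neither document states a cut-point, a number of groups, or a rule such as median or tertiles.

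Cox regression appears only in the missing-data text (SAP 7.6, repeated in Protocol 8.5), where the time-to-event analyses "will be based on a log-rank test or on Cox regression tests". It is not assigned to the biomarkers.

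The biomarker set is "All patients included in FAS who has been evaluable for biomarker status", with no size given. SAP 7.2 and 7.8 label all efficacy analyses exploratory. SAP 7.8 applies a q-value at 10% to subgroup analyses and says nothing about trying several cuts on one marker. SAP 9 records that accrual was closed after the interim analysis by a funder's decision; the final number of patients is not stated.

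**The concern.** A log-rank test compares groups, so a continuous level has to be cut before it can be used. The other option left open, a log transformation, does nothing for the named tests: it does not change who falls above or below a given cut, and it does not change the ranks that Spearman uses. The undefined grouping is therefore the only choice that affects the result.

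Two things are at stake. Even a well-behaved grouping discards information, which matters most in a small sample. And if the grouping were settled after the marker levels had been linked to PFS, the p-value would no longer have its nominal meaning. The q-value step would not repair this: it takes valid p-values as input, and the smallest p-value over several cuts of one marker is not valid unless the search is accounted for.

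**Working it through.** **What the plan lets us reproduce.** There is no stated level, power, cut or event count for the biomarker-PFS test. The only design figure is the two-stage rule for response in SAP 6.4: "If there are 11 or fewer responses in these 21 patients, the study will be stopped", and later "The null hypothesis will be rejected if 45 or more responses are observed in 73 patients". The rejection probability is the sum over x = 12 to 21 of P(X1 = x) × P(X2 ≥ 45 − x), with X1 ~ Bin(21, p) and X2 ~ Bin(52, p). This gives 0.0249 at p = 0.50 and 0.9004 at p = 0.70, agreeing with the stated 0.025 and 90%. Here the design serves only to set the range of N, from about 21 to 73.

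**Assumptions, none from the documents unless noted.** Standard normal log level; exponential PFS; two-sided 5% test. For the 1.65 case, median PFS is 12 months with censoring at 18 months (close to the 78 weeks of follow-up: 78 × 7 / 30.4 = 18.0). The expected event fraction with no effect is 1 − 2^(−18/12) = 0.646, so 13.6 events at N=21 and 47 at N=73.

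**Information kept by a median split.** The mean log level differs between the two halves by 2√(2/π) = 1.596 SD. With equal halves the relative information is (1/4) × 1.596² = 2/π = 0.64, a loss of about 36%.

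Analytic check at hazard ratio 1.5 per SD (β = 0.405) and 51 events:
- continuous: Φ(√51 × 0.405 − 1.96) = 0.825;
- median split: Φ(√(51/4) × 0.405 × 1.596 − 1.96) = 0.637.

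At 15 events the same formulas give 0.348 and 0.240.

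**Simulated power when the log hazard is linear in the log level.** The 1.3 to 1.5 rows have about 69% events.

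| HR per SD | N | Median split | Continuous Cox |
|---|---|---|---|
| 1.65 | 21 | 26% | 40% |
| 1.65 | 40 | 47% | 67% |
| 1.65 | 73 | 73% | 91% |
| 1.5 | 21 | 21% | 30% |
| 1.5 | 40 | 37% | 54% |
| 1.5 | 73 | 57% | 78% |
| 1.4 | 73 | 44% | 63% |
| 1.3 | 73 | 33% | 46% |

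**Simulated false positives with no effect**, N from 21 to 73 and 50-90% or more events:

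| How the test is formed | Rejects at nominal 5% |
|---|---|
| Cox on the continuous level | 4.9-6.2% |
| Median split fixed in advance | 4.8-6.5% |
| Best of median and two tertiles | 11-15% |
| Best cut in middle 50% of values | 21-28% |
| Best cut in middle 60% | 25-32% |
| Best cut in middle 80% | 33-44% |

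**Where Cox does not win.** If the truth is a step at the median with hazard ratio 2, the split has 66% power against 55% for Cox at N=73, and 23% against 20% at N=22. With a U-shaped effect both tests reject only about 5-6% of the time.

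**The case against.** The strongest reply is that the documents never say a cut will be searched for. That is correct. A reader might infer from the open sentence that the plan carries a false-positive rate of a quarter or more. The text does not support that: it is silent on method, and a cut fixed in advance holds the error near 5%. The inflated rates describe what is not excluded, and they depend on the search window, the sample size and an assumed 5% level.

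A reader might also infer that Cox regression is better in every case. It is not. The power gain above comes from data generated under log-linearity, and a true step at the median reverses it.

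Nor is the whole secondary objective compromised. Protocol 2.2 frames the question around response, and for response the Spearman correlation uses the ungrouped level. Only the PFS route is affected, and the SAP lists these markers as exploratory.

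It can also be said that mentioning a log transformation, together with Cox in SAP 7.6, hints at a continuous model. The hint is fair, but neither is assigned to this analysis, so the named test remains the log-rank. Finally, at stage 1 size both approaches have low power (26% and 40% even at hazard ratio 1.65), so the change does not rescue the question there.

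What stands is that the named method forces a grouping, that the grouping has no rule, and that the exploratory label and the q-value do not supply one.

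**Conclusion.** The point holds as a low-priority correction to an exploratory analysis. The stated test cannot use a continuous level without a cut, and no cut is defined. Under approximate log-linearity a fixed median split costs about 36% of the information, or roughly 9 to 21 percentage points of power in the cases tabulated. If the cut were chosen from the data, which is neither planned nor excluded, false positives would be about 11% to 44% at an assumed two-sided 5% level, depending on how widely one searched, and the q-value procedure would not correct for it.

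The N=73 figures are the planned case only. With accrual closed early, the biomarker set is probably smaller, but its size is not given. The effect sizes and PFS distribution are assumptions. The primary endpoint and its decision rule are not affected.

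**What to change.** In SAP 7.5, and in the matching text of Protocol 8.2 if that is amended, replace the two sentences on PFS and on transforming or grouping the levels with text such as:

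> Each baseline biomarker level will be related to PFS by a Cox model with the standardised log2 level as a single continuous covariate. The hazard ratio per SD with its 95% confidence interval will be reported, and the likelihood-ratio p-value will enter the q-value procedure of section 7.8. Undetectable levels will be set to [value stated here] before logs are taken. Kaplan-Meier curves split at the median are for display only and will not be tested.

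If a cut-off is wanted in its own right, fix it before the marker data are linked to PFS, or report a p-value corrected for maximal selection.

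The cost is a few sentences. No new data are needed, and the SAP already accepts Cox regression elsewhere. The price is an assumption of approximate log-linearity and some loss of power if the true effect is a step at the median (about 55% against 66% at N=73 with hazard ratio 2).

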4.2 Inclusion criteria

Patient eligibility will be reviewed and documented by a suitable member of the investigator's study team before the patients are enrolled in the study.

Patients must meet all the following inclusion criteria to be enrolled in the study:

- 1. Patient aged 18 years or older.
- 2. Patients with histological confirmation of metastatic, non-squamous or locally advanced non-small cell lung cancer (NSCLC) who are not candidates for local curative treatment, with an activating EGFR mutation and concomitant T790M mutation.
- 3. Patients with an M1a stage according to the TNM version 7 including M1a (malignant effusion) or M1b (distant metastasis), or locally advanced disease that is not a candidate for

Protocol No.: MedOPP112 Protocol date: May 21, 2018 Version 3

curative treatment (including patients who progress after chemoradiotherapy in stage III disease).

- 4. Patients with an EGFR deletion or mutation in exon 19, exon 21 (L858R, L861Q) or exon 18 (G719X) and concomitant T790M mutation before treatment confirmed centrally.
- 5. ECOG (Eastern Cooperative Oncology Group) performance status less than or equal to 2.
- 6. Existence of measurable or evaluable disease (according to RECIST 1.1 criteria). Patients with asymptomatic and stable brain metastases are eligible for the study.
- 7. Possibility of obtaining sufficient tissue sample, via a biopsy or surgical resection of the primary tumor or metastatic tumor tissue, if no systemic treatment has been performed for advanced or metastatic disease from sample collection to enrollment in the trial.
- 8. Life expectancy ≥12 weeks.
- 9. Adequate hematologic function: Absolute neutrophil count (ANC) >1.5 x 109/L, platelet count >100.0 x109/L and hemoglobin >9.0 g/dL (>6.2 mmol/L).
- 10. Appropriate coagulation (INR ≤1.5).
- 11. Adequate liver function: Total bilirubin <1.5 × ULN, ALT and/or AST <2.5 × ULN, alkaline phosphatase <5 ULN, except in the presence of single bone metastases and in absence of any liver disorders.
- 12. Adequate renal function: Calculated creatinine clearance >50 mL/min (Cockcroft-Gault) and proteinuria <2+ (dipstick).
- 13. Capacity to swallow, patient capable of completing treatment and accessible, ensuring proper follow-up.
- 14. Patients able to complete study and within geographical proximity allowing for adequate follow-up.

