5 STUDY ASSESSMENTS AND PROCEDURES

5.1 Screening phase: Patient enrollment procedures

Study-specific assessments performed during the screening phase: Day 0 (patient enrollment pending re-confirmation of EGFR and confirmation of T790M in the central laboratory), Day 14 maximum (to confirm T790M during days 1-14) and Day 28 (to confirm remaining screening criteria during Days 15-42 after Day 0 of the screening phase).

Written informed consent from the patient must be signed before performing any study procedure.

By giving their consent, patients will be informed as to the nature of the study drug and will receive pertinent information regarding the study objectives, possible benefits and potential adverse events. They will also receive information on the follow-up procedures and possible risks they will be exposed to. This document also informs patients about how biological samples will be obtained and collected and its legal implications. After receiving the document, the patient will read it (or receive information verbally before witnesses) and will sign the previously approved informed consent. The patient will receive a signed copy of the informed consent. The patient can withdraw their consent and discontinue the study; this will not affect any future medical treatment.

Once this consent is obtained and upon confirmation that the patient meets the remaining screening criteria (through the available data in the medical history or by performing the corresponding necessary tests), the investigator staff will submit the tumor tissue samples (accompanied by the anatomy-pathology report) and serum/plasma to the central reference laboratory immediately for central evaluation of activating EGFR mutations and T790M mutation in exon 20. The characteristics and packaging of biological sample shipments are described in "Appendix 4: Instructions for shipment of biological samples to the central laboratory" of this protocol.

Within 7 working days, the central reference laboratory will inform as to whether there is sufficient material that is suitable for EGFR analysis and determination of T790M mutation.

- A. If tissue quality and/or quantity is deemed unacceptable by the central reference laboratory, the study staff will be suitably informed and if a sample of tumor tissue cannot be obtained under better conditions, the patient will not be eligible for the study.

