4. INTRODUCTION

4.1 Preface

We can state that in EGFR-mutation-positive NSCLC, in addition to the molecular diagnosis, it is necessary to quickly validate and implement a kit as part of clinical practice for the detection of a predictive biomarker panel that will allow for adequately personalized treatments using EGFR TKIs in monotherapy. To this end, we propose to begin a phase IIa clinical trial of osimertinib (AZD9291) in patients with a recent diagnosis of NSCLC with EGFR mutations and with the concomitant pre-treatment T790M mutation. The mutation will be detected in tumor tissue using a highly sensitive assay for T790M, based on laser microdissection and a peptide-nucleic acid clamping PCR.

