Appendix 2 List of protocol deviations

Description	Category	Deviation excludes from analysis set?		
		Full Analysis / safety set	Per protocol set	Biomarker analysis set
Informed consent form not signed	Inclusion/Exclusion criteria	Yes	Yes	Yes
Outdated versions of informed consent signed	Inclusion/Exclusion criteria	Case by case	Case by case	Case by case
IMP no administered	Treatment	Yes	Yes	Yes
Without histological confirmation of locally advanced or metastatic, non-squamous non-small cell lung cancer (NSCLC).	Inclusion/Exclusion criteria	No	Yes	No
Without an activating EGFR mutation.	Inclusion/Exclusion criteria	No	Yes	Yes
Without concomitant T790M mutation.	Inclusion/Exclusion criteria	No	Yes	Yes
Patients without a M1a stage or M1b or locally advanced disease for which there is curative treatment	Inclusion/Exclusion criteria	No	No	No
ECOG>2	Inclusion/Exclusion criteria	No	No	No
No measurable or evaluable disease (as per RECIST 1.1 criteria). With the exception of pts with asymptomatic and stable brain metastases.	Inclusion/Exclusion criteria	No	Yes	No
Patients without having a pre-dose and a postdose valid result.	Biomarkers	No	No	Yes
Life expectancy <12 weeks.	Inclusion/Exclusion criteria	No	Case by case	No
Adequate organ function	Inclusion/Exclusion criteria	No	Case by case	No
Without capacity of swallow or complete the study.	Inclusion/Exclusion criteria	No	Case by case	No
No relevant toxicities at baseline	Inclusion/Exclusion criteria	No	Case by case	No
Patients who have received prior antineoplastic treatment for advanced disease.	Inclusion/Exclusion criteria	No	Case by case	No
Second active neoplasia	Inclusion/Exclusion criteria	No	Case by case	No

<6 months with prior treatment with cytotoxic chemotherapy for advanced NSCLC.	Inclusion/Exclusion criteria	No	Case by case	No
Patients who have received prior EGFR treatments for lung cancer.	Inclusion/Exclusion criteria	No	Case by case	No
Patients who have received treatment with an investigational drug within 3 weeks before the first day of study treatment.	Inclusion/Exclusion criteria	No	Case by case	No
Treatment with prohibited drugs within 14 days before the first day of study treatment.	Inclusion/Exclusion criteria	No	Case by case	No
Prohibited concomitant medication	Efficacy and safety	No	Case by case	No
Hypersensitivity to IMP	Investigational Medicinal Product	No	Case by case	No

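### McNemar's test has no meaningful null for tumor-tissue T790M, or for the activating EGFR mutation as a class, because every patient in the biomarker set is positive at baseline by design

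*SAP*

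**What the plan says.** SAP 7.5 states that the presence of mutations and the levels of biomarkers, in tissue or blood, "will be compared from baseline to time of progression with the Mc Nemar and Wilcoxon tests, respectively": McNemar for presence and Wilcoxon for levels. Protocol 8.2 has the same sentence. Neither names a mutation, sets one aside, or gives the alpha level or the variant of the test.

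Baseline status in tissue is fixed elsewhere:

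- Inclusion criterion 4 (Protocol 4.2, SAP 6.3.1) requires an activating EGFR mutation and a "concomitant T790M mutation before treatment confirmed centrally".
- The specimen is tissue. SAP 4.1: "The mutation will be detected in tumor tissue using a highly sensitive assay for T790M". Protocol 5.1 adds that when the material is inadequate, "if a sample of tumor tissue cannot be obtained under better conditions, the patient will not be eligible for the study".
- SAP Appendix 2 has a row "Without concomitant T790M mutation", and a matching row for the activating mutation. Both exclude the patient from the biomarker set. SAP 7.4: "Biomarker analysis will be performed on biomarker analysis set".

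Blood is treated differently. SAP 5.2.3 lists "A progress curve showing the EGFR mutational status (including the T790M mutation) in plasma and serum longitudinally" as an endpoint, but no rule requires a positive blood result at baseline.

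**The concern.** McNemar's test uses only patients whose status changes, and asks whether gains and losses are equally frequent. Among patients selected because the first tissue test was positive, there is nobody who can gain the mutation. That selection also removes the opposite-direction errors that would normally offset misses on the repeat test. Every later negative, whether a real loss, a sampling miss or an assay miss, counts the same way.

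Mechanisms of acquired resistance are a secondary objective (Protocol 2.2), and the fate of T790M at progression is a natural part of that question. A small p-value here would probably be read as evidence that treatment clears T790M-positive disease. The planned test cannot bear that reading.

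**Working it through.** The plan states no figure for this analysis, so there is none to reproduce.

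**Inputs.** Baseline-positive proportion in tissue: 100% of the biomarker set (criterion 4 and Appendix 2). Stage 1 and total sample size: 21 and 73 (SAP 6.4). Not in the documents, so assumed: two-sided alpha 0.05; number of tissue pairs n, shown from 10 to 73; and the rate f at which a still-positive tumor tests negative on re-biopsy, shown from 5% to 20%.

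**Step 1: the null.** Equal gains and losses is the same as equal positive proportions at the two times. With 100% positive at baseline, the null says that no later test is ever negative. One later negative already contradicts it.

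**Step 2: the p-value with b losses and 0 gains.** Exact: p = 2 × 0.5^b. Mid-p: 0.5^b. Chi-square on 1 df: the statistic is b uncorrected, and (b − 1)²/b with continuity correction. The number of pairs appears in none of these.

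| b | exact | mid-p | chi-square | corrected chi-square |
|---|---|---|---|---|
| 4 | 0.125 | 0.0625 | 0.0455 | 0.134 |
| 5 | 0.0625 | 0.031 | 0.025 | 0.074 |
| 6 | 0.031 | 0.016 | 0.014 | 0.041 |
| 8 | 0.008 | 0.004 | 0.005 | 0.013 |

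The fewest losses for p<0.05 are 4 (uncorrected chi-square), 5 (mid-p) or 6 (exact, or corrected chi-square). Since n drops out, 6 of 10 (60.0%) and 6 of 73 (8.2%) both give exact p = 0.031.

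**Step 3: chance of p<0.05 with no true loss.** The number of later negatives is Binomial(n, f). For the exact test the chance is P(at least 6):

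| n | f = 5% | 10% | 15% | 20% |
|---|---|---|---|---|
| 10 | <0.1% | <0.1% | 0.1% | 0.6% |
| 15 | <0.1% | 0.2% | 1.7% | 6.1% |
| 21 | <0.1% | 1.4% | 8.3% | 23% |
| 40 | 1.4% | 21% | 57% | 84% |
| 73 | 16% | 75% | 97% | 99.8% |

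For the uncorrected chi-square it is P(at least 4). At n = 21 this is 1.9%, 15%, 39% and 63%.

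**Step 4: comparison where gains are possible.** With equal discordance of 5% to 20% in each direction, the exact test's type I error is 0.04% to 2.0% at n = 21 and 1.7% to 3.0% at n = 73. The losses needed for p<0.05 rise to 8 with one gain, 10 with two and 12 with three. The test behaves properly there.

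**The case against.** Two stronger readings are tempting, and the documents support neither.

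- A reader might infer that the whole McNemar analysis is invalid. The sentence covers blood as well as tissue, and a tissue-positive patient may be plasma-negative at baseline and positive later. C797 and other acquired mutations can also be gained. No single activating type (del19, L858R, L861Q, G719X) is required of every patient, so only the class is fixed.
- A reader might infer that the test will call T790M loss significant whether or not it is real. It will not: with the exact test, 0 to 5 losses are not significant. If repeat testing were perfect, any loss would be real and no change would give no discordant pairs. The error arises only through misses.

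The size is also uncertain. SAP 4.1 calls the assay highly sensitive and gives no miss rate. Protocol 5.2 makes re-biopsy a recommendation only, although Protocol 3.2 and SAP 6.1 say that one should be done. SAP 9 records that accrual closed after the interim review. Forty pairs may be optimistic, and with 21 or fewer pairs, a miss rate of 10% or less and the exact test, the risk is small.

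The endpoints are exploratory (SAP 5.2.3, 7.8), and the decision rule in SAP 7.10 uses only the primary endpoint. A proportion with an interval carries the same repeat-test misses as the test does.

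All of this stands as a limit on scope and weight. It does not supply a meaningful null for the two fixed comparisons. Nor does the 10% q-value that SAP 7.8 applies to subgroup analyses, because a multiplicity adjustment cannot repair a p-value computed against the wrong reference.

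**Conclusion.** The point holds for tumor-tissue T790M and for the activating EGFR mutation as a class, in the biomarker set. There the gain cell is empty by construction, and the p-value reflects only whether about 4 to 6 later negatives occurred. It can mislead; it need not. With no true loss, the exact test's chance of p<0.05 runs from 1.4% (21 pairs, 10% misses) to 84% (40 pairs, 20% misses). Those figures rest on an assumed alpha, miss rate and number of pairs. The empty cell follows from the documents alone. This is a minor correction to an exploratory analysis and does not touch the primary result.

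**What to change.** Add one sentence to SAP 7.5 and Protocol 8.2. For tissue T790M and the activating EGFR mutation as a class, report the number and proportion no longer detected among patients with a valid re-biopsy, with a Clopper-Pearson 95% CI and no McNemar test. For example, 6/21 is 28.6% (11.3% to 52.2%), whereas 6/73 is 8.2% (3.1% to 17.0%); McNemar gives both the same p-value. Describe the result as not detected rather than lost, because it includes repeat-test and sampling misses, which the interval does not correct.

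Keep McNemar for blood and for mutations that eligibility does not fix, such as C797, and state which variant and alpha will be used. The change needs no new data, and its cost is the wording.
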